#### 7.5.8 Discontinuation of PEG-ADA one month after infusion of gene modified cells

PEG-ADA will be continued until one month (+/- 6 days) post-infusion of gene-modified cells. PEG-ADA will be restarted if i) the child is withdrawn from the study ii) if after 180 days there is no evidence of gene modified cell engraftment and/or failure of T cell recovery.

PEG-ADA may be restarted at PI's discretion prior to this time point on clinical grounds e.g. infective problems or delayed T cell reconstitution. In instances when PEG-ADA has been restarted, PEG-ADA may be withdrawn again, if the patient remains well and meets withdrawal criteria (i.e. has detectable PBSC ADA activity and/or detection of gene modified cells above baseline levels).

## 8 Evaluation and Follow-up

### 8.1 Assessment of safety and efficacy

#### 8.1.1 Immunological reconstitution

Detailed analysis of immune recovery following gene therapy for primary immune deficiency is essential to evaluate the effectiveness of the procedure, and is largely beyond the scope of our routine clinical immunology resources. We have therefore established dedicated resources and methodologies that enable us to 1) measure the diversity and complexity of T and B reconstitution 2) analyse thymic education and output following gene modification of lymphocyte precursors and 3) measure cellular antigen specific responses.

The analyses will be carried out on pre- and post-treatment samples as shown in Appendix 5. The results will be interpreted as a change in value over time through a longitudinal analysis, for each patient.

- The lymphocyte subset counts (LSC) immunophenotyping panel will be carried out to show the distribution of cells and is used to detect an increase in naïve CD3+ T lymphocyte cell numbers and assess the development of normal distribution of cell populations. This will include the evaluation of CD3+, CD19+, CD16+, CD56+, CD3+, CD4+, CD8+ and naïve CD4+CD45RA+CD27+ cell numbers.
- B cell memory tests will be performed at months 12, 24, and 36. This parameter should be recorded as “not done” in the CRF for subjects that have already completed any of these three visits at the time of amendment (Version) implementation.
- TCR excision circles (TRECs) may be enumerated as a surrogate marker for new thymic emigrants following gene therapy.
- Whole blood lymphocyte proliferation assays will be carried out to test function of T cells and will include responses to mitogens (PHA stimulation and CD3 stimulation).
- Representation of TCR families by flow cytometric analysis (V $\beta$  phenotyping), also forms an important part of monitoring for both physiological and potentially pathological clonal expansions.
- Restoration of antibody production (IgA, IgM, IgG), and serological responses to tetanus vaccinations will be assessed.

#### 8.1.2 Metabolic correction

Metabolic assays will be carried out at the Purine Research Laboratory and will include analysis of red blood cell ADA activity, dATP and dAdo levels. These will indicate how effectively gene therapy has corrected the metabolic phenotype of ADA-SCID.

### **8.1.3 Molecular characterisation of gene transfer**

Molecular characterisation of gene transfer in patient cells is also an important parameter for assessment of efficiency, and potentially for assessment of safety:

- Quantification of transgene copy numbers is determined on sorted cell populations by real-time PCR methodology. This will be performed on peripheral blood samples and on bone marrow samples (if available). Detailed integration analysis maybe used to investigate specific clonal expansions.
- Analysis of lentiviral vector integration sites will be performed by specialised PCR based techniques and by high throughput sequencing of lineage specific populations. This will be performed on peripheral blood samples and on bone marrow samples (if available). These assays will be performed at the times specified in appendix 5.

## **8.2 Investigations and monitoring schedule**

See appendix 5 for tables of investigations.

### **8.2.1 Pre-treatment investigations**

Pregene therapy visit will be carried out prior to gene therapy. This visit will include pre-treatment monitoring investigations, which should be carried out within 3 months of the start of gene therapy treatment according to Appendix 5

### **8.2.2 Post-infusion monitoring**

Patients will be monitored on protocol at 1 month, 6 weeks, 3, 6, 9, 12, 18, 24, 30 and 36 months post-infusion. Window to carry out these visits is +/- 5 days for visits at 1 month, 6 weeks and +/- 2 weeks for visits at 3, 6, 9, 12, 18, 24, 30 and 36 months. Follow-up as part of the routine clinical care of post-transplant patients will be annual after this.

Monitoring, testing being performed and information to be collected on CRF are fully detailed in Appendix 5. Modifications to this protocol will be adopted as necessary to improve sample-processing capability, and a degree of flexibility regarding the actual dates of assessment will be maintained. Additional tests may be carried out in the event of a significant adverse effect to ensure optimal clinical care.

### **8.2.3 Safety monitoring**

The safety of treatment will be summarised using AEs, laboratory assessments and clinical examination assessments. These will be analysed continuously from pre-gene therapy to study completion, depending on the data available. Further details are given in the SAP

#### **8.2.4. Neurological and behavioural monitoring of patients**

Cognitive and behavioural defects are well documented in ADA-SCID patients following HSCT (Rogers et al., 2001; Titman et al., 2008). It is thought that patients undergoing gene therapy will also suffer similar consequences.

We have recently set up a study protocol (funded by the Department of Health) to assess all immunodeficiency patients (both ADA-SCID and non ADA-SCID) for cognitive, educational and behavioural outcomes following HSCT. This assessment will therefore also be applied to all ADA-SCID patients undergoing gene therapy. In addition to this, we will administer a standard health related quality of life questionnaire to assess the general impact of the treatment on the child functions.

### **8.3 Treatment failure/lack of response**

- Failure of immune reconstitution is determined by poor recovery of T lymphocyte numbers and function by day 180

OR

- by absence of gene corrected cell engraftment (<0.1 %) tested by quantitative PCR in peripheral blood and/or BM samples 6 months after the procedure.
- If there is no immune recovery/evidence of gene modified cell engraftment seen 180 days after gene therapy, PEG-ADA will be commenced OR the patient will undergo stem cell transplant from a matched unrelated donor depending on the clinical state of the child.
- If there is no matched unrelated donor available, the patient will be commenced on PEG-ADA OR if the referring health agency is unable to provide funding, the patient will undergo stem cell transplant from an unrelated or haploidentical parental donor.
- In the absence of a matched family or unrelated donor a second administration of the gene therapy treatment could be considered following specific approval from GTAC/MHRA on a case by case basis.

### **8.4 Withdrawal of individual subjects**

A patient can withdraw or be withdrawn from protocol treatment in the study at any time from enrolment until the transduced CD34+ cells have been administered. Once a patient has been administered the transduced CD34+ cells study treatment is complete.

- Patients from whom  $<3 \times 10^6$  CD34+ cells/kg are harvested for the back-up, will be withdrawn from the study prior to conditioning and offered a repeat harvest
- Patients from whom  $<1 \times 10^6$  CD34+ cells/kg are harvested for transduction, will be withdrawn from the study prior to conditioning and offered a repeat harvest
- If less than  $0.5 \times 10^6$  viable transduced CD34 + cells/kg are returned to the patient, then back-up bone marrow/PBSCs will be returned and patients will be withdrawn from the study
- If after 180 days there is no evidence of the transgene in PBMCs by qPCR or there is no evidence of T cell recovery, then patients will re-start PEG-ADA and will be withdrawn from the study

PEG-ADA may be restarted at PIs discretion prior to this time point on clinical grounds e.g infective problems or delayed immune reconstitution and at this stage will be withdrawn from the study. The decision for patients to remain off PEG-ADA is dependent on a combination of factors including:

- 1) metabolic detoxification as assessed by sustained red blood cell dATP levels  $<250$  umol/l
- 2) T cell recovery as assessed by absolute T cell numbers (CD3+ cells)  $>300$  cells/mm^3
- 3) engraftment of gene modified cells as assessed by vector copy number in CD3+ cells  $>0.05$  ( $>5\%$  of total T cells)

Subjects who wish to discontinue from the study at any time are free to do so. However the reasons for discontinuation should be documented by the investigator if possible.

Patients who withdraw from the study after administration of the transduced CD34+ cells for reasons other than those given above will be encouraged to have follow-up investigations so that the consequences of the administration can be documented and analysed.

Any patient withdrawn prior to administration of transduced CD34+ cells will be replaced in the study.

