PEG-ADA may be restarted at PIs discretion prior to this time point on clinical grounds e.g infective problems or delayed immune reconstitution and at this stage will be withdrawn from the study.

[figure not shown]

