## 8.5 Off study criteria

A patient will be considered off study under the following circumstances:

1. The patient is withdrawn from the study prior to administration of transduced CD34+ cells
2. The patients/parent/guardian withdraws consent for study procedures and data collection
3. The patient is lost to follow-up

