#### **8.8 Trial stopping criteria**

The trial will be stopped prematurely under the following circumstances:

1. Evidence of oncogenesis in any trial patient. The trial will only be re-started following agreement from both the MHRA and GTAC.

The events below will result in halting of the trial and will require a formal evaluation of the reasons for non-efficacy. The trial will only be re-started after discussion with and approval from the MHRA and GTAC:

1. Unsuccessful transduction of 3 consecutive patient CD34+ cells to specified criteria
2. No evidence of vector integration in 3 consecutive patients at 6 months post-treatment
3. 3 consecutive patients needing to re-start enzyme replacement therapy prior to 1 year post-gene therapy

*(From our experience of these studies, 3 consecutive patients would be seen as a number whereby this could not have happened by chance and is most likely related to processes or procedures)*

4. Emergence of new therapies for ADA-SCID, believed by the CI to be of greater benefit to this population of trial patients. The CI is in regular contact with other experts in the field of ADA-deficiency therefore is aware of new developments in the field. Regular reviews of the currently available treatment options for the subject population will be conducted by the PI throughout the trial.

Complete cessation of the trial would be made in consultation with the MHRA and GTAC.

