### **8.3.1.3 Engraftment**

Engraftment of transduced cells will be assessed using vector gene marking in granulocytes, PBMC, CD3, CD34, CD19 and myeloid progenitor cells. Any assessments in which the result indicates that cells were not detected, will be assigned a value of 0.

The vector copy numbers in each type of cell will be summarised for IMP treated subjects by visit using descriptive statistics. In addition, for each cell type, plots of the median and range for copy numbers over time on a logarithmic scale will be produced along with individual subject plots.

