### **8.3.1.4 Cellular and Humoral Immune System Recovery**

Immune reconstitution will be assessed using lymphocyte subsets. Absolute numbers and percentages of CD3+, CD4+, CD8+ CD4+CD45RA+CD27+ T-lymphocytes, CD19+ B-lymphocytes and CD16+CD56+ NK cells will be measured.

For each of the lymphocyte subsets, the actual values and change from baseline will be summarized by visit for each of the IMP treated groups using descriptive statistics. The median value and range will be plotted by treatment group over time on a logarithmic scale and individual counts will be plotted along with the age-dependent normal ranges provided by the study site.

In addition, statistical testing of the change from baseline to 6 and 12 months will be performed for the IMP treated subjects. If the difference is normally distributed, a paired t-test will be used. Otherwise, the Wilcoxon signed rank test will be used.

The trend over time in the IMP treated subjects will be examined for each count separately, using mixed models for repeated measures (MMRM) with visit and baseline count as fixed effects, and subject as a random effect, utilizing the compound-symmetry covariance structure. If counts are approximately normally distributed they will be analysed on the original scale. Otherwise, if log transformation can normalize the data, statistical analysis will be performed on log-transformed data. If the data are still not normal, the data will be ranked in ascending order of magnitude and the analysis will be performed on the ranks.

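### Protocol 8.4 to 8.6 leave scheduled data collection undefined for infused children withdrawn for failure; if it stops, the by-visit primary summaries lean towards responders

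*Protocol*

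**What the plan says.** **Withdrawal.** Protocol 8.4 gives these grounds for withdrawing a child who has already been infused:

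- fewer than 0.5 x 10^6 viable transduced CD34+ cells/kg returned;
- the day-180 rule: "If after 180 days there is no evidence of the transgene in PBMCs by qPCR or there is no evidence of T cell recovery", in which case PEG-ADA is restarted and the child is withdrawn;
- an earlier restart at the investigator's discretion, for "infective problems or delayed immune reconstitution and at this stage will be withdrawn from the study".

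Protocol 4.1 repeats all three.

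**Follow-up after withdrawal.** Section 8.4 then says that patients who withdraw after infusion "for reasons other than those given above will be encouraged to have follow-up investigations", so that the effects of the infusion can be documented and analysed. Section 8.5 has three off-study reasons. The first is "The patient is withdrawn from the study prior to administration of transduced CD34+ cells"; the others are withdrawal of consent and loss to follow-up. Section 8.6 stops assessments and CRF entry for withdrawals before infusion and for withdrawn consent. Section 11.4.4 states lifelong follow-up for all patients, with SAR and SUSAR reporting continuing after study closure.

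**Analysis.** SAP 5.1 makes copy number, T-cell and immunoglobulin measures, dATP and ADA activity primary endpoints at each visit. SAP 8.3.1.3 plans that "The vector copy numbers in each type of cell will be summarised for IMP treated subjects by visit using descriptive statistics". SAP 8.3.1.4 adds that "statistical testing of the change from baseline to 6 and 12 months will be performed for the IMP treated subjects", with a mixed model for the lymphocyte counts. SAP 8.3.1.5 treats the metabolic measures by visit, and 8.3.2.4 does the same for TREC. The sensitivity analyses in SAP 8.3.4 concern major protocol violations only.

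**The concern.** The one sentence in 8.4 that asks infused patients to continue follow-up leaves out those withdrawn for failure. No other section says whether their scheduled tests go on. Two sites of reading, both reasonable, would handle the same child in opposite ways.

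This matters because the trigger for withdrawal is closely tied to the endpoints. A child leaves because the transgene is absent or T cells have not recovered, and copy number and T-cell number are primary endpoints at every visit. If that child's later values are never collected, the remaining children at each later visit have been selected on the outcome being summarised. Selection can begin before month 6, through a low returned dose or an early PEG-ADA restart.

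Scheduled safety data are affected in the same way: integration analysis, RCL testing and full adverse event recording after withdrawal have no stated rule. Under the Appendix 5 footnote, some stored samples are analysed only if the 1-year or 3-year sample is positive. A child with no study sample after day 180 might never trigger that analysis.

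**Working it through.** The plan gives no figure of its own on this point, so the check has two parts: a comparison of the rules, then an illustration of size.

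**1. Rules for an infused child withdrawn for failure**

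- Protocol 4.1 and 8.4: withdrawn from the study.
- Protocol 8.4, follow-up sentence: not covered, because it applies only to other reasons.
- Protocol 8.5: not among the off-study reasons.
- Protocol 8.6: neither stopped nor continued.
- Protocol 7.5.8: a child back on PEG-ADA may come off it again given detectable ADA activity or gene-modified cells, so some testing is expected.
- Protocol 11.4.4: lifelong follow-up, with only SAR and SUSAR reporting named.

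Scheduled collection is therefore contradictory or undefined; it is not explicitly ended.

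**2. What the SAP would do if values stop**

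- Copy number: SAP 8.3.1.3 sets a result with no cells detected to 0, but a visit that never happens contributes nothing.
- Lymphocytes: the paired test at 12 months uses those measured. The mixed model uses observed month-6 values, which helps in part, but it covers lymphocyte subsets only and relies on data being missing at random.
- ADA activity, dATP and TREC: by-visit descriptive statistics with no rule for withdrawn children.
- Overall survival (8.3.1.1): a child withdrawn before 12 months and last known alive has unknown status and is excluded from the proportion.
- Event-free survival (8.3.1.2): death, PEG-ADA reinstitution and second transplant are events, so these failures are counted.

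**3. Effect on the 12-month proportions**

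Assume 10 treated children (SAP 7.1), all alive at 12 months, with 3 withdrawn alive at day 180 after restarting PEG-ADA. When all of n survive, the exact 95% lower limit is 0.025^(1/n).

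- Withdrawn children excluded: 7/7, lower limit 0.025^(1/7) = 0.590, so 59-100%.
- All followed: 10/10, lower limit 0.025^(1/10) = 0.692, so 69-100%.
- Event-free survival either way: 7/10, exact 95% CI 34.8-93.3%.

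**4. How many children might be involved (illustration only)**

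Protocol Table 1 gives off-enzyme counts in earlier trials: 14 + 4 + 3 + 4 = 25 of 17 + 8 + 6 + 5 = 36, or 69.4%, which matches its total. Take the failure rate f as 11/36, with a range from 3/17 to 4/8 by centre and an assumed 10%. Failures among 10 are Binomial(10, f).

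If failures would have had values near zero and contribute none, the by-visit mean is inflated. The mean over all infused is (1 - f) x m, where m is the responder mean; the mean over those remaining is m. The ratio is 1/(1 - f).

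| f | Expected of 10 | P(at least 1) | P(at least 3) | 1/(1 - f) |
|---|---|---|---|---|
| 10% (assumed) | 1.0 | 65.1% | 7.0% | 1.11 |
| 3/17 = 17.6% | 1.8 | 85.7% | 25.3% | 1.21 |
| 11/36 = 30.6% | 3.1 | 97.4% | 63.2% | 36/25 = 1.44 |
| 4/8 = 50% | 5.0 | 99.9% | 94.5% | 2.0 |

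The near-zero assumption suits copy number best. It is doubtful for lymphocytes, because Protocol 3.2.2.1 describes an initial rise in T-cell counts on PEG-ADA.

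**The case against.** The strongest reply is that the documents nowhere say collection stops. Section 8.5 does not take these children off study, 8.6 does not end their assessments, and 7.5.8 expects some to be retested. That is right, and it makes the selection conditional on how 8.4 is applied.

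It can also be said that failures are already visible. Event-free survival counts them, SAP 8.1.2 lists each withdrawal with its reason and time since infusion, the general methods report the number of subjects in continuous summaries, and individual plots are planned for copy number, lymphocytes and ADA/dATP. With 10 children a truncated line would be seen. All of this stands and limits the harm, but it does not make the later summaries representative of all infused children.

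The failure rate is borrowed from gammaretroviral trials with different PEG-ADA timing and busulfan dosing and with follow-up from 0.1 to 10.5 years. It is not a rate of failure by day 180. This also stands, so the numbers in the table are illustrations.

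Three stronger readings are not supported:

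- A reader might infer that failures are the only children not asked to continue. Section 8.6 also stops assessments when consent is withdrawn, which can be after infusion.
- A reader might infer that failures drop out of late safety monitoring. Section 11.4.4 promises lifelong follow-up of all patients, 9.2.2 plans annual RCL samples during care at the hospital, 11.4.3 requires immediate reporting of transgene-related proliferation, and the safety population is all treated subjects. What is undefined is the scheduled study sampling.
- A reader might infer that withdrawn children escape the oncogenesis stopping criterion in 8.8. Its wording, "Evidence of oncogenesis in any trial patient", naturally includes a withdrawn trial child.

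**Conclusion.** The point holds as a gap to be reconciled. Protocol 4.1 and 8.4 withdraw infused failures, 8.4 leaves them out of its follow-up request, 8.5 and 8.6 do not settle their status, and the SAP has no rule for their later visits.

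If collection stops at withdrawal, the by-visit engraftment, immune and metabolic summaries lean towards responders, and the 12-month survival proportion loses children withdrawn alive. Event-free survival is not affected in this way.

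The size is uncertain. Inflation of a mean such as copy number runs from 1.11 at 10% failure to 2.0 at 50%, with 1.44 at 11/36. This assumes that every failure leaves before the visit in question, would have had a value near zero and contributes no data. The survival example assumes 3 of 10 withdrawn and no deaths. The direction for copy number does not depend on the rate chosen. This is a cheap clarification worth making and does not show that the late results will be wrong.

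**What to change.** **Protocol.** Reconcile 4.1, 8.4, 8.5, 8.6 and 11.4.4. State that an infused child who meets a failure criterion or restarts PEG-ADA is recorded as a treatment failure but stays on the scheduled assessments and eCRF to month 36, leaving the study only for a reason in 8.5. No PEG-ADA, rescue or other treatment rule needs to change. A child who stays on study is no longer classed as withdrawn, so the survival proportion in SAP 8.3.1.1 keeps that child.

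**SAP 8.3.1.3 to 8.3.1.5 and 8.3.2.4.** Report the by-visit n out of all infused. Show values after PEG-ADA restart or second transplant separately. In any responder percentage, keep failures in the denominator as non-responders.

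**Cost.** Amendment wording and a few extra scheduled visits, at most about three children's worth at the 11/36 rate. These may be harder for children referred from abroad, since 5.1 accepts referrals worldwide. The late summaries may look less favourable.

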**Total number of participants planned:**

Patients treated with gene therapy on trial: Up to 10 treated patients

The trial will include two other sub-groups: patients treated with gene therapy off trial under GOSH Special License constituting the Compassionate Use Program (CUP) and patients treated with Haematopoietic Stem Cell Transplantation (HSCT) constituting the historical control group.

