### 4.1 Patients treated with gene therapy (on study)

- Patients will be selected on the basis of inclusion and exclusion criteria as detailed below
- A back-up harvest will be retained in case of failure of reconstitution following conditioning and re-infusion of transduced cells
- For the transduction protocol (see appendix 3 for schematics), CD34+ cells will be purified from G-CSF mobilised Peripheral Blood Stem Cell (PBSCs) recovered by leukapheresis (Plerixafor may be added to enhance mobilization), whenever possible or from bone marrow harvested under general anaesthetic. Back-up cells of  $3 \times 10^6$  CD34+ cells/kg will be stored from a single procedure if sufficient cell counts available (and if not previously stored). The remaining CD34+ cells will be taken forward for transduction. If  $< 3 \times 10^6$  CD34+ cells/kg are harvested from the back-up, the patient will be withdrawn from the study

- Patients in whom of  $<1 \times 10^6$  CD34+ cells/kg are available for transduction will not proceed to conditioning, will be withdrawn from the study and will be offered a repeat harvest in approximately. 3 months
- Patient conditioning will be initiated immediately after bone marrow or PBSC collection (busulfan iv. weight adjusted dose)
- After purification, CD34+ cells will be immediately transduced with the lentiviral vector as detailed below, then evaluated for sterility, cell count, and viability, and immediately infused into patients
- Several other tests for safety including testing for RCLs will be performed on re-infused cells and results will be recorded retrospectively
- If less than  $0.5 \times 10^6$  viable transduced CD34+ cells/kg are returned to the patient, then back-up bone marrow/PBSCs will be returned and patients will be withdrawn from the study
- PEG-ADA will be withdrawn one month (+/- 6 days) post-infusion
- If there is no bone marrow recovery by 6 weeks (ANC $<0.5 \times 10^9/L$  or platelets  $< 20 \times 10^9/L$ ) the back-up harvest will be re-infused
- Patients will be followed up on study at 1 month, 6 weeks, 3, 6, 9, 12, 18, 24, 30 and 36 months post gene therapy. Visit windows will be +/- 5 days for visits at 1 month, 6 weeks and +/- 2 weeks for visits at 3, 6, 9, 12, 18, 24, 30 and 36 months post gene therapy If after 180 days there is no evidence of the transgene in PBMCs by qPCR or there is no evidence of T cell recovery, then patients will re-start PEG-ADA and will be withdrawn from the study

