### **7.5.6 Patient conditioning regimen**

During transduction of CD34+ cells, patient will commence conditioning. Patients will receive non-myeloablative conditioning with intravenous busulfan. Busulfan dose will be weight-dependent, in accordance with the recommendation below (table taken from (Bartelink et al., 2012)).

Body-weight	mg/kg/day
3 to 15kg	5.1
15 to 25kg	4.9
25 to 50kg	4.1
50 to 75kg	3.3
75 to 100kg	2.7

A wash-out period of at least 24 hours will be maintained prior to reinfusion of the transduced cells. Pharmacokinetic monitoring of busulfan levels will be performed after administration of the first dose.

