#### **8.6 Follow-up of withdrawn subjects**

Patients withdrawn from the study prior to administration of transduced CD34+ cells and patients for whom consent has been withdrawn for the study, will resume normal clinical care. Efficacy and safety assessments will not be carried out from the point of withdrawal and data will not be recorded in the Case Report Forms (CRFs).

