#### 8.9.1 Analysis populations

There will be 3 populations analysed in this study: The on-study patients treated with IMP (gene therapy), patients who were treated under compassionate use (CUP patients) and the historical comparator group of patients who received HSCT.

The safety analysis population will include all patients who received the IMP infusion, including both on-study patients and patients who were treated on a compassionate use basis. In addition, all the allogeneic HSCT controls patients (with any type of donor) will be included.

Further efficacy populations will be detailed in the statistical analysis plan (SAP).

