#### **Efficacy**

##### Primary Endpoints

Statistical methodologies for comparing gene therapy to historical controls at all stages will be descriptive in nature and will utilize the following approaches:

1. OS and EFS will be described using Kaplan-Meier curves for patients treated with investigational gene therapy product and HSCT, respectively, and statistically compared by the log-rank test and proportional hazards models (where applicable).
2. OS and EFS rates post treatment will be described by group and their differences between groups presented along with associated exact binomial confidence intervals.

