#### **9.1.2 Infection**

Withdrawal of PEG-ADA can have adverse effects on immunity, as well as on other organ systems. Once PEG-ADA is withdrawn, the numbers of circulating T, B, and NK lymphocytes will decline and may remain low for several months until the autologous transplant of gene-corrected CD34+ cells leads to immune reconstitution. It is possible that a severe infection may develop during this time and this could even be fatal if it does not respond to therapy. If immunity is severely decreased after discontinuation of enzyme replacement therapy and the subject experiences multiple or serious infections, then therapy may have to be resumed.

It is also possible that the cells for infusion could become infected with bacteria or fungus during the growth period in the laboratory. If there is any evidence of infection of the cells with unwanted agents and busulfan has already been administered, the cells will be returned to the subject with appropriate antibiotic cover. If the infection significantly affects viability (to a total cell dose of  $<0.5 \times 10^6/\text{kg}$ ) then transduced cells will not be returned and the back-up

bone marrow will be infused. However, there is a remote chance that subjects could acquire a bacterial or fungal infection from the re-infused cells (this also applies to the back-up cells, if administered).

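### Children given busulfan whose product is then not infused are replaced, left out of every efficacy and safety population, and not recorded after withdrawal

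*Protocol*

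**What the plan says.** - **Timing of conditioning.** Protocol 7.5.6: "During transduction of CD34+ cells, patient will commence conditioning". Section 4.1 likewise starts conditioning straight after collection. Busulfan is therefore given before the final product is known.
- **Product not returned.** Protocol 9.1.2 covers contamination found after busulfan. The cells normally go back under antibiotic cover. If viability falls so far that the dose is below 0.5 x 10^6/kg, "then transduced cells will not be returned and the back-up" marrow is infused instead. Section 9.1.6 is similar.
- **Low dose returned.** Protocol 4.1, repeated in 8.4, covers a dose below the same threshold: if fewer than that number of "viable transduced CD34+ cells/kg are returned to the patient, then back-up bone marrow/PBSCs will be returned" as well, and the child is withdrawn.
- **Replacement.** Protocol 8.4: "Any patient withdrawn prior to administration of transduced CD34+ cells will be replaced in the study". There is no exception for a child already conditioned.
- **Recording.** Protocol 8.6, on withdrawal before administration: "Efficacy and safety assessments will not be carried out from the point of withdrawal and data will not be recorded" in the case report forms. Section 7.5.2 repeats this, and 8.5 classes the child as off study.
- **Populations.** Protocol 8.9.1: "The safety analysis population will include all patients who received the IMP infusion". SAP 7.1 and 7.2 also define the gene-therapy side of each population as IMP-treated subjects.
- **Objective.** Tolerability of the conditioning regimen is a secondary objective (Protocol 4.2.2, SAP 4.2).

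**The concern.** A child who has had busulfan but receives no gene-modified cells bears the risk of conditioning without the intended benefit. That child's course bears directly on the tolerability of conditioning and on how well the strategy works once a family is committed to it. Under the rules above, another child takes the place and the course after withdrawal goes unrecorded. Two things are at stake: the completeness of the safety data on conditioning, and whether the reported EFS describes children who start conditioning or only those whose product was infused. With about ten patients, one child is enough to change the picture.

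**Working it through.** **1. Is there a figure in the plan to reproduce?** No. The target is "Patients treated with gene therapy on trial: Up to 10 treated patients", with no power calculation, and Protocol 8.9.2 says: "Statistical methodologies for comparing gene therapy to historical controls at all stages will be descriptive in nature". The check is mainly of text.

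**2. Trace one child through the rules.** The child is harvested successfully and starts busulfan (4.1, 7.5.6). The product is contaminated and falls below threshold, so it is not returned (9.1.2). Section 9.1.2 does not itself use the word withdrawn. However, no study treatment has been given and follow-up visits are timed from infusion (8.2.2), so withdrawal before administration is the natural reading. The child is then replaced (8.4), off study (8.5) and unrecorded (8.6). Even without formal withdrawal, the child is outside every population, because each requires the IMP (8.9.1; SAP 7.1, 7.2).

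**3. What survives?**
- SAP 8.1.1 uses enrolled subjects as denominator and lists each exclusion with its reason. A count and a reason survive.
- SAP 8.4.1.2 and 8.4.1.3 list events before infusion, and Appendix 5 starts adverse-event reporting at the treatment visit. Events before withdrawal may survive. This is not certain, because Protocol 11.1 defines an adverse event for a patient administered an IMP.
- SAP 8.1.2 summarises withdrawals among treated subjects, so this child is not in it.
- SAP 8.2.13 summarises conditioning among IMP-treated subjects only.
- SAP 8.3.4 triggers sensitivity analyses by major protocol violations. A child handled as the protocol directs is not one.
- SAP 5.2 leaves transduction feasibility to the study team, outside the SAP.

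None of these yields toxicity, survival or PEG-ADA use after withdrawal.

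**4. Possible size (hypothetical).** Assume 10 infused children, of whom x are event-free at 1 year, and k conditioned but uninfused children counted as EFS failures. The proportion is x/(10 + k), with Clopper-Pearson 95% limits.

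| k | x = 10 | x = 9 |
|---|---|---|
| 0 | 10/10 = 100% (69.2-100) | 9/10 = 90.0% (55.5-99.7) |
| 1 | 10/11 = 90.9% (58.7-99.8) | 9/11 = 81.8% (48.2-97.7) |
| 2 | 10/12 = 83.3% (51.6-97.9) | 9/12 = 75.0% (42.8-94.5) |
| 3 | 10/13 = 76.9% (46.2-95.0) | 9/13 = 69.2% (38.6-90.9) |

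**5. Would the stopping rule reveal it?** Protocol 8.8 halts the trial after three consecutive unsuccessful transductions. Let p be an assumed chance of product failure per conditioned child, and suppose each failure counts towards that rule. Before the tenth infusion:
- P(at least one failure) = 1 - (1 - p)^10
- expected failures = 10p/(1 - p)
- P(three in a row) = 1 - (1 - p^3)^10

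| p | At least one | Expected | Three in a row |
|---|---|---|---|
| 5% | 40.1% | 0.53 | 0.1% |
| 10% | 65.1% | 1.11 | 1.0% |
| 20% | 89.3% | 2.5 | 7.7% |
| 25% | 94.4% | 3.33 | 14.6% |

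The documents give no value of p. The table shows only that isolated failures would seldom trigger the rule.

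**The case against.** The strongest reply is that the gap is narrow and may be empty. That stands. The only explicit route to a conditioned but uninfused child is contamination that brings the dose below threshold. The documents report no such case, and SAP 7.1 speaks of 10 subjects as already recruited.

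A reader might also infer more than the text supports:

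- **That manufacturing failures vanish from the results.** They do not. The disposition table, the exclusion listing and the listings of pre-infusion events keep a trace. What is lost is the later course.
- **That the earlier London programme supplies a failure rate.** Protocol 3.2.5 reports failure in 3 of 7 patients, one from a poor harvest and two from low transduction. Those were treated patients. In this trial harvest shortfalls lead to withdrawal before conditioning (8.4), and transduction efficiency is tested only after infusion (7.5.5), so it cannot stop an infusion.
- **That failed products are moved out of sight into the compassionate-use group.** Appendix 9 does list failure to meet release specification as a reason for that route. But patients infused under it are in the safety population and the secondary efficacy population (SAP 7.1, 7.2).
- **That overall survival is inflated.** A child who receives back-up cells and survives is not a death.

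Two technical objections are also fair. OS and EFS run from transplant in both groups (SAP 8.3.1.1, 8.3.1.2), and controls are defined by having been transplanted, so an all-conditioned set has no matching control denominator. Counting back-up infusion as an event would also capture infused children given back-up for non-recovery at 6 weeks (4.1). The remedy has to respect both points.

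Finally, 4.1/8.4 and 9.1.2 have different triggers, which softens the conflict. It does not remove it: the dose threshold is the same, and the handling decides whether the child counts as infused.

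**Conclusion.** The point holds in a limited form. Followed as written, the plan loses toxicity, survival and PEG-ADA use after withdrawal for any child who starts busulfan and is not infused. It keeps no more than a count, a reason and any earlier events. This sits badly with a secondary objective on tolerability of conditioning.

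The size is unknown and may be zero. If all 10 infused children were event-free, each of the first three uninfused children counted as a failure would lower EFS by about 9, 8 and 6 points in turn (100 to 90.9 to 83.3 to 76.9%). This rests on the assumed counts and on treating non-infusion as a failure. OS is unaffected unless such a child dies.

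The infused-only primary analysis remains legitimate for what it describes. This is an inexpensive improvement to safety recording and transparency, not a defect that invalidates the main comparison.

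**What to change.** 1. **Recording and safety population.** Amend Protocol 7.5.2, 8.6 and 8.9.1 and SAP 7.2 so that every child who starts busulfan has adverse events and survival recorded. Summarise safety from the start of conditioning, with uninfused children shown separately.
2. **One supportive table.** Keep infused on-study subjects as the primary efficacy population. Add a single-arm OS/EFS table in all on-study children who start conditioning, with time zero at the start of conditioning and non-infusion of the IMP counted as an EFS event. The event needs this explicit definition: PEG-ADA continues until one month after infusion (7.5.8), so an uninfused child might never stop it and would show no reinstitution under SAP 8.3.1.2. State that the HSCT controls have no matching all-conditioned denominator and make no comparison from this table.
3. **Reconcile the text.** Bring Protocol 4.1 and 8.4 into agreement with 9.1.2 on handling of below-threshold product, and say how the resulting children are classified for analysis. Which handling is right is for the clinical team.
4. **If there were no such children,** say so in one sentence of the report; the supportive table is then unnecessary.

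The cost is a change of population wording, continued case-report-form entry for any such child, one extra table, and possibly a lower EFS in that table.
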